**Evaluation of cognitive state in seniors using
Neurosteer single-channel EEG with an auditory assessment tool**

Clinical Research Center
Neurosteer Ltd.

Protocol
Version 1.0
04:2022
March 2022

Protocol Summary

OBJECTIVE	To evaluate the ability to differentiate between cognitive states in the senior population using a single-channel EEG with an interactive assessment tool.
STUDY DESIGN	This is an observational study. Patients who fulfill all inclusion criteria and none of the exclusion criteria will be enrolled in the study, be neurologically evaluated and will go through EEG recordings while listening to auditory instructions and performing cognitive and functional tasks. EEG recordings will be analyzed using proprietary computational analyses.
STUDY POPULATION	The study population is comprised of senior patients.
SAMPLE SIZE CONSIDERATIONS	90 subjects
INCLUSION CRITERIA	
 1. Men and women over the age of 50. 2. MMSE ≥ 10. 3. Patient is able to collaborate. 4. No seizure events.
EXCLUSION CRITERIA	
 1. Advanced stage of cognitive decline (MMSE < 10). 2. Any verbal or non-verbal form of objection from patient or form patient's family member or significant other. 3. Significant hearing impairments. 4. Significant vision impairments. 5. Damage to integrity of scalp and/or skull. 6. Skin irritation in the facial and forehead area. 7. Epilepsy or seizure activity. 8. History of drug abuse.

STUDY PROCEDURES	Clinical staff will identify potential subjects and will examine the eligibility of subjects according to inclusion and exclusion criteria. Research staff will inform the patient or legal guardian/ family/ accompanying individuals on study's objective and design. Patients will sign the Informed Consent Form (ICF). Research staff will set up an initial assessment session using the Neurosteer system. In this session the patient will listen to the auditory assessment battery and perform cognitive tasks. Over the next 7 days, clinical staff will set up another session using the Neurosteer system. In this session the patient will listen to auditory instructions and perform two PASS sub-tasks: a drug sorting task and a phone use task. Level of cognition will be assessed by validated screening tools (MMSE and MoCA) and the Neurosteer technology.
DATA TO CAPTURE	
The following data will be collected for the purposes of this study:
 
Demographics: age, gender, year of education.
 
Clinical data: official diagnosis, comorbidities, drugs, MMSE score, MoCA score, GDS score, CLOX score, PASS drug sorting and phone use sub-scores.
 
Medical history: number of years with the disease, date of surgery.
 
Measurements of the research: electrophysiological data captured by Neurosteer system.

TECHNICAL DESCRIPTION OF THE SYSTEM	The system is composed of hardware and software modules that facilitate the capture and interpretation of electrophysiological data as well as enable viewing the processed data in real time and offline. An electrode patch is attached on the subject's forehead to capture the electrophysiological signal. The signal is sent via low energy Bluetooth to an EEG Monitor. The signal is then sent via Wi-Fi to the cloud where the data is stored on a HIPAA compliant server. Data analysis performed in the cloud transforms the electrophysiological signal into easily readable data of brain activity, which is accessible via any web interface. The brain activity features (BAFs), which comprise the main novelty of the method, are created using a variant of the wavelet packet analysis and the best basis algorithm. Statistical analysis will be performed on the data.
STATISTICAL ANALYSIS PLAN	MMSE and MoCA scores will be taken from previous evaluations performed in the institute. Each patient will be evaluated using the continuous measurement by the Neurosteer system. Statistical analyses will include Pearson correlations between electrophysiological data and MMSE and MoCA scores, and reaction times in the tasks. Linear mixed models (LMM) will be calculated with group and task level as independent variables.

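### Age is collected but enters no named analysis, so the planned tests can show overall discrimination but cannot separate cognitive state from age

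*Combined protocol and SAP*

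**What the plan says.** All references are to the Protocol Summary.

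- **Statistical Analysis Plan.** Two analyses are named. The first: "Statistical analyses will include Pearson correlations between electrophysiological data and MMSE and MoCA scores, and reaction times in the tasks". The second: "Linear mixed models (LMM) will be calculated with group and task level as independent variables". No covariate, partial correlation, stratification or age subgroup is mentioned.
- **Data to Capture.** Age is recorded: "Demographics: age, gender, year of education". So are other patient characteristics: "Clinical data: official diagnosis, comorbidities, drugs, MMSE score, MoCA score, GDS score".
- **Study Design and Inclusion Criteria.** "This is an observational study", and eligibility covers "Men and women over the age of 50". No upper age limit or matching is stated.
- **Objective.** "To evaluate the ability to differentiate between cognitive states in the senior population using a single-channel EEG with an interactive assessment tool".

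Apart from the data list, age appears only in the inclusion criterion.

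**The concern.** Patients are not randomised to a cognitive state. If older patients tend to score lower and the EEG features also vary with age, the EEG will correlate with MMSE and MoCA, and will differ between groups, even if it says nothing about cognition once age is known. That age relates to both measures is an assumption; the documents report no such correlation.

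What is at stake is the reading of a positive result. Reported as overall discrimination, it is answered by the planned tests. Read as the EEG tracking cognition rather than age, it is not supported by any named analysis. The second reading is a natural one, because Study Procedures lists the Neurosteer technology next to MMSE and MoCA as a means of assessing level of cognition.

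The main effect of task level is a within-subject comparison and is largely unaffected. The group effect, and any group-by-task interaction, is exposed if the groups differ in age. No confounding route is claimed here for education or gender.

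**Working it through.** **Inputs.** From the documents: n = 90. Assumed: a two-sided 5% level, standardised normal variables, and every correlation with age. The sample size has no stated derivation, so there is no figure of the plan's own to reproduce.

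**Step 1: critical values.** With t the 97.5% point on the given degrees of freedom, the critical |r| is t/√(df + t²). This gives 0.207 unadjusted (88 df) and 0.208 with age partialled out (87 df).

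**Step 2: correlation produced by age alone.** Take the extreme case of no EEG–score link given age. The marginal correlation is then, in absolute size, r(EEG, age) × r(score, age). By Fisher's z, the chance of significance is Φ(m − 1.96) + Φ(−m − 1.96), with m = atanh(r) × √(90 − 3). For age correlations of 0.4 with both: r = 0.4 × 0.4 = 0.16, m = 0.1614 × 9.327 = 1.505, and the chance is 32.5%.

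| Age correlation with both | Induced r | Unadjusted, Fisher z | Unadjusted, simulated | Age-adjusted, simulated |
|---|---|---|---|---|
| 0.2 | 0.04 | 6.6% | 6.6% | 5.0% |
| 0.3 | 0.09 | 13.4% | 13.1% | 4.9% |
| 0.4 | 0.16 | 32.5% | 32.6% | 5.1% |
| 0.5 | 0.25 | 66.4% | 67.0% | 5.1% |

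The simulations used 40,000 replicates. The excess over 5% is a false-positive rate only for a claim beyond age; the marginal association itself is real in these scenarios.

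**Step 3: unequal links.** With age correlations of (EEG, score), the simulated unadjusted rates (20,000 replicates) are:

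- (0.2, 0.4): 11.5%
- (0.2, 0.5): 15.8%
- (0.3, 0.5): 29.3%
- (0, 0.5): 4.8%

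Age-adjusted rates are 4.8% to 5.2%. A variable linked only to the score leaves the unadjusted test at about 5%, so both links are needed.

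**Step 4: group comparison.** The documents define neither the groups nor the random effects, so no figure can be given for the mixed model itself. For a simple test of two assumed groups of 45, the spurious standardised difference is the age gap in SD × the EEG–age correlation. An age gap of 0.5 to 1 SD and a correlation of 0.3 to 0.5 give 0.5 × 0.3 = 0.15 up to 1 × 0.5 = 0.50. The unadjusted test is then significant in 11% to 66% of studies.

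**Step 5: effect of adjusting on power.** Assume a marginal r of 0.30 and age correlation a with both measures. The partial correlation is (0.30 − a²)/(1 − a²); for a = 0.4 this is 0.14/0.84 = 0.167. Unadjusted power is about 83% (simulated; 82.3% by Fisher's z).

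| a | Partial r | Power, age-adjusted | Power, also adjusting for education and gender |
|---|---|---|---|
| 0.2 | 0.271 | 73.7% | 72.5% |
| 0.3 | 0.231 | 59.4% | 58.2% |
| 0.4 | 0.167 | 34.3% | 33.8% |
| 0.5 | 0.067 | 9.6% | 9.5% |

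Almost all of this fall comes from the part of the association shared with age. If the correlation stayed at 0.30 after adjustment, the lost degree of freedom alone would take power only from 82.3% to 81.9%.

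**Step 6: what age adjustment leaves behind.** Add a factor independent of age and correlated 0.2, 0.3 or 0.4 with both EEG and score, with age correlations of 0.4. The age-adjusted test is still significant in 7.4%, 16.7% or 43.7% of studies. The rate returns to 4.7% to 5.0% only if that factor is also adjusted for.

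**The case against.** The strongest reply is that the plan makes no claim beyond age. Its objective is to differentiate cognitive states, which is a marginal question, and the named analyses address it. This stands: the point is conditional on how results are read, and it does not make the planned tests invalid.

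Second, the list of correlation analyses is worded as open, and age is collected, so an adjusted analysis could still be run. That is true, but none is named, and one chosen after the data are seen is weaker evidence than one fixed beforehand.

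Third, every figure rests on assumed correlations and on the extreme case of no link given age. At 0.2 on both links the excess is under 2 percentage points, and with either link absent it vanishes. This also stands: the range shows what could happen, not what does happen in this study.

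Fourth, the groups are undefined, so whether they differ in age cannot be judged. That is a prior gap in the plan, and it leaves the mixed-model part of the concern conditional.

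Finally, age is not the only candidate. Drugs, comorbidities and GDS score are also collected, and Step 6 shows that other factors can matter after age adjustment. This limits what an age-adjusted result may claim; it is not a reason to leave age out.

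**Conclusion.** The concern holds. Age is recorded, neither named analysis uses it, and no stated design feature takes the place of adjustment. The plan can therefore show that the EEG discriminates overall, but not that it carries information about cognition beyond age.

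The omission is certain; its size is unknown. Under the assumptions above, the unadjusted correlation test would be significant in anything from about 5% (one age link absent) to 67% (0.5 on both) of studies with no EEG–score link given age, against about 5% after adjustment. The objections bear on how serious the point is, not on whether it is true. It should be fixed, with medium confidence in its practical importance.

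**What to change.** Pre-specify age as a fixed effect in the mixed model, and report age-adjusted partial correlations (or the equivalent regressions) beside the planned unadjusted Pearson correlations. State that the unadjusted results describe overall discrimination, and that any claim of information beyond age rests on the adjusted estimates. Do not present age adjustment as removing all confounding. Years of education and gender may be added as optional covariates, at a cost of about 1 percentage point of power under the assumptions in Step 5.

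No new data are needed. The cost is that adjusted associations may be smaller and less often significant, as the Step 5 table shows. Because the adjusted estimate answers a different question, it should accompany the unadjusted one and not replace it.
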